# **Study Protocol and Statistical Analysis Plan**

**Active vent Performance Study – ID# 366**

**May 11, 2022**

**NCT04774185**

# Active vent Performance Study – ID SRF-366

## 1 Objectives and hypotheses of the clinical investigation

### 1.1 Purpose of the clinical investigation claims for clinical performance, effectiveness or safety of the investigational device that are to be verified

(P) The patient problem is own-voice amplification with closed vents. (I) A conventional solution are open dome fittings. However the side effect is reduced low frequency sound processing in hearing aids, and thus reduce sound processor benefit. Sonova has introduced an active vent feature based on a new RIC with an internal actuator that controls a physical venting mechanism. (C) Thus the investigation will focus on the comparison between hearing aids fitted with the new active vent over an open dome. (O) The active vent is expected to provide

- a. Improved speech intelligibility when listening to speech in noise using beam-forming in a closed-vent condition,
- a. Improved sound quality of streaming music and speech when in a closed-vent condition, and
- b. Comparable own-voice comfort in an open-dome condition.

### 1.2 Primary and Secondary Objectives

Primary Objective:

Evaluate whether Phonak Audéo P90-R in combination with an ActiveVent (AV) receiver provides better speech intelligibility for speech in noise than Phonak AudéoP90-R with a standard receiver and an appropriate\* standard dome AND providing natural sound in everyday listening situations for people with mild to moderate hearing loss.

Secondary Objective(s):

Evaluate whether Phonak Audéo P90-R in combination with an ActiveVent (AV) receiver improves listening effort compared to Phonak AudéoP90-R with a standard receiver and an appropriate\* standard dome in everyday listening (communication) situations for people with mild to moderate hearing loss.

Evaluate whether Phonak Audéo P90-R in combination with an ActiveVent (AV) receiver provides same own voice perception than Phonak Audéo P90-R with a standard receiver and an appropriate\* standard dome for people with mild to moderate hearing loss.

Evaluate whether Phonak Audéo P90-R in combination with an ActiveVent (AV) receiver improves sound quality compared to Phonak AudéoP90-R with a standard receiver and an appropriate\* standard dome when listening to streamed music and speech for people with mild to moderate hearing loss.

## **2 Design of the clinical investigation**

### **2.1 General**

#### **2.1.1 Design Type**

The study will be a single-blinded randomized cross-over design. The comparison of devices will be done within participant, whereby each participant will be asked to perform a behavioral assessment using both fitting modalities, active vent and open dome.

#### **2.1.2 Procedures**

#### **2.1.3 Investigation-related Procedure**

Participants will not be treated for hearing loss. A standard PTA will be administered during the appointment for the purpose of candidature screening and fitting the hearing aids for testing. The hearing aids will be fitted to match NAL-NL2 targets, using standard audiometric procedures.

## **3 Statistical design and analysis**

### **3.1 Determination of Sample Size**

Power analysis using published data [Keiser et al., International Journal of Audiology Volume 52, 2013 - Issue 11] suggest that to reach sensitive of 1 dB shift in intelligibility thresholds between RIC closed to open states, the study requires  $N = 21$  (Z-statistics), at  $\delta = 1.41$  dB,  $\alpha = 0.05$ ,  $\beta = 0.1$ .

Due to the low sensitivity of the intelligibility test we planned to include 26 participants

### **3.2 Statistical criteria of termination of trial**

Describe the criteria for the termination of the trial or the stopping rules. Trial will be terminated if the participant is not able to

1. If this not possible to reach convergence in the adaptive intelligibility test, which requires a standard error of 0.8 dB SNR.

### **3.3 Planned Analyses**

The statistical analysis plan includes the methods and types of the analysis, the variables the data sets and the timeframe when the (interim) analysis is planned.

#### **3.3.1 Datasets to be analyzed, analysis population**

n/a

#### **3.3.2 Primary Analysis**

A linear mixed effect model will be used to analyze the intelligibility and sound quality benefits. The fixed effects in this model will be fitting modalities (AV: closed, AV vent open, Open dome), average hearing loss (in dB HL), and order of feature tested (first or second). The random effect will be a subject-specific intercepts. This analysis will be conducted by the PI.

#### **3.3.3 Secondary Analysis**

ANOVA for own voice investigation.

This analysis will be conducted by the PI.

Amendment will be done if the protocol of the home trial is developed.

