### **3.3.4 Interim Analysis**

Analysis is done on regular basis for updating the sponsor on the available data set.

=> no final conclusions!

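### The own-voice objective is sameness, but the only analysis planned for it is an ANOVA for a difference, with no margin or criterion that could support sameness

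*Combined protocol and SAP*

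**What the plan says.** Section 1.1 lists as an expected outcome "Comparable own-voice comfort in an open-dome condition". Section 1.2 turns this into a secondary objective: to evaluate whether the active vent receiver "provides same own voice perception than Phonak Audéo P90-R with a standard receiver" and a suitable standard dome. The other objectives in section 1.2 are worded as superiority (better intelligibility, improved listening effort, improved sound quality). Own voice is the only one worded as sameness.

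For the analysis, section 3.3.3 says "ANOVA for own voice investigation" and adds only who will do it and that an amendment will follow if a home-trial protocol is developed. It names no outcome scale, conditions, contrast, hypothesis or decision rule. The mixed model in section 3.3.2 does not cover own voice: "A linear mixed effect model will be used to analyze the intelligibility and sound quality benefits". The sample size in section 3.1 is set for a 1 dB shift in intelligibility threshold, not for own voice. Section 3.3.4 provides for repeated looks: "Analysis is done on regular basis for updating the sponsor on the available data set", with a note that no final conclusions are drawn from them.

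**The concern.** An ANOVA tests the null hypothesis of no difference between conditions. Failing to reject that null has two explanations that the test cannot separate: the fittings are alike, or the study was too imprecise to tell. Conversely, a small but significant difference would not show that the fittings fail to be comparable. Neither outcome answers the question in section 1.2.

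The plan does not say that a non-significant result will be read as sameness; that is an inference. But with no margin or interval criterion, it is the only route the plan offers to the objective. The point has weight because section 1.1 opens with own-voice amplification as the patient problem. The case for the device is better intelligibility without loss of own-voice comfort, and this analysis carries the second half.

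**Working it through.** **The plan's own figure.** The only sample size calculation is for intelligibility. Reading 1.41 dB as the SD of the paired difference, with a 1 dB shift, two-sided α = 0.05 and 90% power:

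n = [1.41 × (1.960 + 1.282) / 1]² = 20.89, rounded up to 21.

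This reproduces the stated N = 21. The planned number is higher: "Due to the low sensitivity of the intelligibility test we planned to include 26 participants". Neither figure says anything about own voice.

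**Inputs for the illustration.** n = 26 is from section 3.1. The paired setting is from section 2.1.1: "The comparison of devices will be done within participant". Everything else is assumed, because the documents give no own-voice scale, SD, margin or dropout rate: two conditions, a roughly continuous score, two-sided 0.05, all 26 contributing, and differences in units of the SD of the paired difference.

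**Step 1: how often a real difference is missed.** With two within-subject conditions the ANOVA amounts to a paired t test on 25 degrees of freedom. Its critical value is 2.060, and the non-centrality is d × √26.

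| True difference d (SD) | Non-centrality | P(non-significant) |
|---|---|---|
| 0.3 | 1.53 | 69% |
| 0.4 | 2.04 | 50% |
| 0.5 | 2.55 | 31% |

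**Step 2: how often sameness would be shown.** Two one-sided tests (TOST) at 0.05 each are equivalent to requiring the 90% confidence interval to lie inside ±margin. The expected half-width is about t(0.95, 25)/√26 = 1.708/5.099 = 0.335 SD. TOST power comes from integrating over the sampling distribution of the SD. Non-inferiority power, one-sided at 0.05, comes from the noncentral t distribution. With no true difference:

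| Margin (SD) | TOST power | Non-inferiority power |
|---|---|---|
| 0.4 | 27% | 63% |
| 0.5 | 60% | 80% |
| 0.6 | 82% | 91% |
| 0.7 | 93% | 97% |

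At a margin of 0.6 SD, a true difference of 0.1 or 0.2 SD lowers TOST power from 82% to 76% or 62%.

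**Step 3: compare the two criteria.** With no true difference, the difference test is non-significant in 95% of trials by construction, yet only 60% meet the interval criterion at ±0.5 SD. So at least 35% of trials (95 − 60) would be non-significant without having shown sameness to that margin.

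**The case against.** The strongest reply is that the fault is the missing criterion, not the model. A within-subject ANOVA yields the same contrast and interval as a random-intercept model when data are complete and balanced and no covariates are added, so a margin and an interval rule could be attached to it. That is right, and it limits what the change of model achieves: the margin and the rule do the work. It does not rescue the plan, which has neither.

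The plan also never states that non-significance will be taken as sameness, and section 3.3.6 lets later additions be justified in the report. The first point is accepted above. The second does not help, because a margin chosen after results have been seen is weak support, and section 3.3.4 has data viewed regularly. The note that those looks carry no final conclusions limits their use, but does not stop own-voice results from being seen.

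The choice of contrast is partly a judgement: section 1.2 does not give the vent state for own voice. Active vent open against open dome follows from sections 1.1 and 3.3.2, but the sponsor should confirm it.

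The figures are generic to any paired comparison of 26 people and may not apply to a short ordinal rating. They are also best-case on numbers: at a 0.6 SD margin with no true difference, TOST power falls from 82% to 77% with 24 contributing and 69% with 21. This makes the illustration optimistic without changing the conclusion.

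**Conclusion.** The concern holds. The objective is sameness, the only named analysis tests for a difference, and nothing elsewhere in the document supplies a margin, contrast or interval rule. This is more than missing detail, since the analysis carried out exactly as written cannot answer the objective. That conclusion rests on the text alone. The percentages rest on the assumptions listed and show the range of consequences, not this trial's actual power. It should be fixed, but it concerns one secondary objective and leaves the primary analysis and the sample size untouched.

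**What to change.** Rewrite section 3.3.3 along these lines:

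- **Outcome and contrast.** Name the own-voice measure and its scale. Estimate the within-subject contrast active vent open minus open dome from a mixed model with subject effects, as in section 3.3.2. If the closed vent is also rated for own voice, report it separately.
- **Margin.** Fix and justify a margin in points of that scale before any own-voice data are viewed, including at the regular looks in section 3.3.4.
- **Decision rule.** Conclude sameness only if the 90% confidence interval lies wholly inside the margin (TOST). If the claim is only that own voice is not worse, use one-sided non-inferiority at 0.05 and reword the objective to match.
- **Power.** State the power at 26 participants for the chosen margin, with the assumed SD.
- **If the margin is tight.** Below about 0.6 SD of the paired difference, TOST power is under about 80% even with no true difference. I would not enlarge the trial for a secondary objective. Report the estimate with its interval, and make no sameness claim unless the interval falls inside the margin.

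If no margin can be justified, reword the objective as descriptive.

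The cost is SAP wording and one justified margin, with no extra participants or tests. The downside is that sameness can no longer be claimed from a non-significant p-value, and with 26 people and a tight margin the result may well be inconclusive.

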### **3.3.4 Interim Analysis**

Analysis is done on regular basis for updating the sponsor on the available data set.

=> no final conclusions!

### **3.3.5 Safety Analysis**

Describe the analysis of the safety parameters that will be done, when and how and by whom it will be done.

In case of reported AEs those will be reported to the ethic committee and the study manager within 24h.

### **3.3.6 Deviation(s) from the original statistical plan**

Any additions or changes of the statistical analysis will be reported in the study report with proper justification.

### **3.3.7 Handling of missing data and drop-outs**

In case of missing data those will be ignored but the remaining data set will be considered in data analysis especially because of the small sample size.

## **4 Informed consent process**

### **4.1 Process for obtaining informed consent**

NAL processing requires participants to be identified from the NAL database or from the Hearing Australia database. All participants listed in the NAL database are volunteers willing to participate in re-research. All participants from hearing Australia are clients of Hearing Australia who have not opted out of research with NAL during their registration to received clinical services.

Regardless of the database source, participants are first contacted by phone, mail or email, depending on their preferred contact methods. An invitation letter is sent to them which describes the task involved and the overall aim of the study. The invitation letter template is attached to the ethics documentation. Their participation is voluntary, but they are told of the payment they will be received upon participation. The payment is calculated based on the effort of the task required by the study, distance of travel requirements to attend the clinic, and urgency of recruitment, e.g., high pay is provided for longer lengths of travel and longer appointments.

Upon responding to mail or email invite letter, participants are contacted, with the preferred method being a phone call unless participants prefer an alternative approach. During this call, participants are given a more detailed description of the task required by the study, appointments times available, and payment methods. At this point, if participants wish to proceed, a time is scheduled to start the appointment.

Upon participant arrival, the first task is to sign off the consent form, as per the ethics application. Before signing the consent form, participants are asked if they have any questions or concerns about the study.

Information is provided as best understood by the clinician at the time.

Suppose that at any time during the appointment the task diverges from protocol and this impacts on timing or data collected. In that case, an explanation is provided to the participant if they are willing to remain for an extra period or stop at the agreed time, with no penalty to payment. Depending on the extension of the additional work, additional payment may be offered.
